15. ADVERSE EVENTS AND SERIOUS ADVERSE EVENTS

15.1. Terms and Definitions

Adverse event (AE) reporting will follow the Health Research Authority (HRA) guidelines on safety reporting in clinical trials that are not of investigational medicinal products (non-CTIMP).

An AE is defined as any untoward medical occurrence in a participant in a research study, including occurrences which are not necessarily related to the administration of any of the research procedures. If serious, as per the definition below, it would be considered a serious adverse event (SAE).

An adverse reaction (AR) is defined as an AE that is deemed to be possibly, probably or definitely related (see table 3, section 15.3, below) to the study procedures (e.g. obtaining BCVA). If serious, as per the definition below, it would be considered a serious adverse reaction (SAR).

A serious adverse event (or reaction) (SAE/SAR) is defined as an untoward medical occurrence that:

- results in death
- is life-threatening
- requires hospitalisation or prolongation of existing hospitalisation
- results in persistent or significant disability or incapacity; or
- consists of a congenital anomaly or birth defect; or
- is otherwise considered medically significant by the investigator

Hospitalisation is defined as an inpatient admission regardless of length of stay, even if the hospitalisation is a precautionary measure for continued observation. However, hospitalisations for a pre-existing condition, including elective procedures for conditions that have not worsened during the trial do not constitute a SAE.

15.2. Adverse Eventing Recording and Reporting

The AE reporting period for the trial begins upon consent and ends at week 52 (the last follow up visit). All reportable unexpected AEs/ARs and SAEs/SARs should be followed until they are resolved. If the event has not been resolved by the time of the participant's 52-week visit, it will be recorded as ongoing.

The PI or designee should record all directly observed AEs/ARs and those spontaneously reported by the participant in trial worksheets (which constitute the data source for the trial), which will then be filed or uploaded in the medical records of the participant, in accordance with GCP.

It is expected that many participants will experience events that are in keeping with pre-existing medical conditions rather than being related to the trial. Events associated with any pre-existing medical conditions that the participant may have when entering the trial will not need to be reported. The exception to this will be death: even if death occurs as a result of the participant's pre-existing condition, death should be reported as a SAE.

Refractive error will be studied in detail as an outcome of the trial. Thus, this will not be reported as an AE. All other, general or specific complications of pars plana vitrectomy, will be reported.

Potential visual field loss will be investigated and confirmed by obtaining a visual field in patients complaining of loss of peripheral vision at any point during the trial. If confirmed, visual field loss will be recorded in the corresponding worksheet.

Treatments used for complications occurring in CORDS will be recorded. If as a result of the occurrence of a complication a participant needs to be admitted to the hospital for treatment, this will be reported as a SAE/SAR.

Development/progression of a cataract in the vitrectomy group will be recorded and reported. Cataracts will be graded following the AREDS classification (16). Development of cataract will be determined when there is progression from no cataract (i.e. Nuclear Sclerosis [NS] and Posterior Subcapsular [PSC] and Cortical Sclerosis [CS] \leq 1) to any cataract (i.e. NS and/or PSC and/or CS >1). Progression of cataract will be considered when there is progression from any cataract to higher stages (i.e. from 1 to any higher grade: 2 or 3) (16).

SAEs will be reported on the SAE form. SAEs should be reported to the NICTU within 24 hours of the investigator becoming aware of the event, by email to [contact]. The site should not wait until all information about the event is available before notifying the NICTU. The NICTU will acknowledge receipt of the SAE form by email. Information not available at the time of the initial report must be sought and submitted to the NICTU as it becomes available. The NICTU will notify the CI of all SAEs reported.

A SAE occurring to a research participant will be reported to the main REC if the event was:

a) Related (i.e. SAR): that is, it resulted from administration of any of the research procedures, and b) Unexpected: that is, the type of event is not listed in the protocol (or in the SmPC of any drugs used) as an expected occurrence.

Reports of related and unexpected SAEs will be submitted to REC within 15 days of the NICTU becoming aware of the event, using the SAE report form for non-CTIMPs published on the HRA website. The CI will include a report on the safety of participants in the annual progress report to REC.

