4. BACKGROUND AND RATIONALE

4.1. Background Information

Rhegmatogenous retinal detachment (RRD) is the separation of the retina from the wall of the eye, where it is normally attached. It affects 10-18 people per 100,000 per year (1,2). Thus, in the UK, with a population of around 68 million (3) there are 6700-12,000 RRD per year.

RRD can lead to permanent central and peripheral vision loss (i.e. total blindness) if not treated in a timely manner. Vitrectomy is the most common surgery done for RRD (4,5). Retinal reattachment following one vitrectomy occurs in 80-88% of eyes, with 59-67% gaining vision above 0.3 LogMAR, which is the vision required to fulfil UK driving standards (4,5).

Data from the British and Eire Association of Vitreo-Retinal Surgeons (BEAVRS) showed that most patients with RRD are phakic; this means that they still have their natural lens (i.e. have not had cataract surgery) (5). Data from the BEAVRS database (unpublished, but accessible to the COMBAT

Doc no: Page 12 of 38 Protocol v1.0 Final 25.02.25 IRAS 338079

research group) showed that of 8436 vitrectomies done in non-high myopic phakic eyes out of 13,900 vitrectomies performed at several sites in the UK, only 10% combined vitrectomy with cataract surgery (called phacovitrectomy) at the time of the RRD repair. Of 664 phakic eyes with at least 12 months follow-up in which combined surgery was not performed at the time of RRD surgery, 320 (48%) were recorded to have a cataract or to have had it already removed within three months of the original vitrectomy. Only 20% of these eyes had their own clear natural lens at 12 months following vitrectomy. Therefore, phacovitrectomy is done in a minority of patients at the time of RRD repair; and many patients have either a cataract present or undergo separate cataract surgery soon after the RRD surgery.

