7.2. Eligibility Criteria

Eligibility for the trial will be confirmed by an ophthalmologist delegated to undertake this task on their site's delegation log. Patients will be eligible if they fulfil the following criteria:

Inclusion Criteria

- Adults >50 years of age
- Non-highly myopic (< -6 diopters; <26.5 mm axial length) phakic RRD
- Naïve to previous vitreoretinal surgery
- Pars plana vitrectomy is planned to repair their RRD.

Exclusion Criteria

- Presence of a "formed/established cataract".
 - A "formed/established cataract" is defined as a cataract that, based on the Age-Related Eye Disease Study (AREDS) Research Group (16), is graded as nuclear sclerosis of ≥ 3 and/or if there is an anterior cortical cataract and/or a subcapsular posterior cataract involving the visual axis.
- Pseudophakia or aphakia.
- High myopia (> -6 diopters; >26.5 mm axial length).
- Giant retinal tear (i.e. presence of one or more retinal tears of >3 clock hours in size).
- Retinal dialysis.
- Participation in an investigational drug study.
- Declined consent for participation.

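### Section 15.2 puts grade 1 in two cataract categories, so development and progression overlap for moves from grade 1, and the progression rule is ambiguous for 2-to-3

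*Protocol*

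**What the plan says.** Protocol section 15.2 makes cataract a reported safety item in one arm: "Development/progression of a cataract in the vitrectomy group will be recorded and reported". The scale is named: "Cataracts will be graded following the AREDS classification (16").

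Two rules follow, in adjacent sentences.

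- **Development.** "Development of cataract will be determined when there is progression from no cataract", where no cataract means nuclear sclerosis (NS), posterior subcapsular (PSC) and cortical (CS) grades all at or below 1. The end state is given as "to any cataract (i.e. NS and/or PSC and/or CS >1").
- **Progression.** "progression from any cataract to higher stages (i.e. from 1 to any higher grade: 2 or 3").

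Section 7.2 sets which lenses can enter. The exclusion for formed cataract is "nuclear sclerosis of ≥ 3 and/or if there is an anterior cortical cataract and/or a subcapsular posterior cataract involving the visual axis". An eye with NS grade 2 can therefore be randomised.

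**The concern.** The development rule splits the scale at grade 1: at or below 1 is no cataract, above 1 is any cataract. The progression rule uses the same term, any cataract, but its bracket starts at grade 1, which the sentence before has just called no cataract. Both cannot hold.

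Two things are at stake. First, an eye that leaves grade 1 can be entered under both headings, so the two rates overlap. Second, an eye that starts at grade 2 and worsens is treated one way by the words of the progression rule and another by its bracket. With at least 30 sites (section 7.1), similar eyes may be classified differently. Lens opacity after vitrectomy alone is part of the trial's rationale (section 4.1), so readers will look at these rates.

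**Working it through.** No figure in the plan needs reproducing; the check is to apply each rule to every possible worsening.

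**Inputs**

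- No cataract: NS, PSC and CS all ≤1 (section 15.2).
- Any cataract: at least one component >1 (section 15.2).
- Progression bracket: start at 1, end at 2 or 3 (section 15.2).
- Entry: NS ≥3 is excluded, so NS 2 is allowed (section 7.2).
- Assumptions: whole grades 0 to 3, with each rule comparing a baseline grade *b* with a later grade *f*.

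**Rules**

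- Development: *b* ≤ 1 and *f* > 1.
- Progression by the bracket: *b* = 1 and *f* = 2 or 3.
- Progression by the words, using the section's own meaning of any cataract: *b* > 1 and *f* > *b*.

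**Result for a single component**

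| Move | Development | Progression, bracket | Progression, words |
|---|---|---|---|
| 0 to 1 | no | no | no |
| 0 to 2 | yes | no | no |
| 0 to 3 | yes | no | no |
| 1 to 2 | yes | yes | no |
| 1 to 3 | yes | yes | no |
| 2 to 3 | no | no | yes |

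Of the six upward moves, two (1-to-2 and 1-to-3) meet both development and bracketed progression. One (2-to-3) meets neither rule by the stated grades and is caught only by the words. If the scale in use has no grade below 1, the first three rows vanish and every development is also a progression by the bracket.

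**After the edit**

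If the bracket starts where the section's own any cataract starts (above 1), the last column replaces the third. Then 0-to-2, 0-to-3, 1-to-2 and 1-to-3 are development only, 2-to-3 is progression only, and 0-to-1 is neither. Each worsening that ends above grade 1 has exactly one label.

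**The case against.** **The words already cover 2-to-3.** This stands in part. The operative phrase does include an eye starting at grade 2, and only the bracket leaves it out. It would be wrong to say that such eyes are lost; a site could count them or not, depending on which half of the sentence it follows.

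**The signs may be misread from the PDF.** Inequality signs do vary elsewhere: the axial-length limit is ≤26.5 mm in the study summary and <26.5 mm in section 7.2. Here an artefact is unlikely. The two signs in the development rule are complementary (≤1 and >1). A sign lost before the 1 in the bracket does not help either: on whole grades a start above 1 is at least 2, and grade 2 could not then be listed as a higher grade reached. Removing the overlap through the development rule would require both of its signs to be wrong, and the bracket would still omit 2-to-3.

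**The item may be reported as one.** Section 15.2 names development and progression together, and in a combined count 1-to-2 appears once. That limits the harm, but the section defines two events, and the bracket still leaves 2-to-3 in doubt in a combined count.

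**A reader might infer more.** One might argue that eyes already operated on by week 52 have no grade and drop out, so that the comparator's cataract burden is understated. The protocol does not support this. Grading is not tied to week 52, safety is assessed at every visit (section 10.3), and cataract surgery is captured separately (sections 10.2, 12.4 and 14.2). How a removed lens counts can be left to the SAP.

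Nor is the registry statement "Only 20% of these eyes had their own clear natural lens at 12 months following vitrectomy" a measure of the error. Applied to 276/2 = 138 comparator participants it gives 0.80 × 138 ≈ 110 eyes without a clear natural lens. That figure does not separate cataract present from cataract removed and says nothing about how many eyes would be misclassified.

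**Conclusion.** The inconsistency is real and lies in the protocol's own text. Grade 1 is on both sides of the boundary, two of six upward moves carry both labels, and 2-to-3 is classified differently by the words and the bracket. As written, the development and progression rates in the vitrectomy arm cannot be interpreted separately.

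The scope is limited. This is a descriptive safety item in one arm; the primary analysis is unaffected. The net direction is not fixed, because double labelling adds to a sum of the two counts while the bracket reading removes 2-to-3. The frequency cannot be estimated, since the protocol gives no distribution of baseline grades; counting types of move is not counting eyes. The conclusion rests on whole grades and on comparing later grades with baseline.

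**What to change.** Edit the progression sentence in section 15.2 so that the two categories are exclusive by baseline status:

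- **Development:** all of NS, PSC and CS at or below 1 at baseline, and any of them above 1 later.
- **Progression:** any of NS, PSC or CS above 1 at baseline, and a later rise in grade, so that 2-to-3 counts. Say explicitly whether the rise may be in any component. If it may, an eye entering with NS 2 whose PSC later goes from 0 to 2 also has a place.

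The cost is a one-sentence edit, with no change to treatment, visits or sample size. The reported development and progression counts will differ from those under the present wording. An eye that starts at or below 1 and worsens through several grades is counted once, as development. The edit is best made before follow-up grades accumulate, so that all sites apply one rule.

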15.3. Assessment of Causality

For unexpected AE/ARs the PI or designee should make an assessment of causality, i.e. the extent to which it is believed that the event may be related to any of the research procedures (Table 3).

Table 3. Categories of Causality for Adverse Events

Category	Definition
Definitely*	There is clear evidence to suggest a causal relationship, and other possible contributing factors can be ruled out.
Probably*	There is evidence to suggest a causal relationship, and the influence of other factors is unlikely.
Possibly*	There is some evidence to suggest a causal relationship (e.g. the event occurred within a reasonable time after administration of a research procedure). However, the influence of other factors may have contributed to the event (e.g. the patient's clinical condition, other concomitant events).
Unlikely	There is little evidence to suggest there is a causal relationship (e.g. the event did not occur within a reasonable time after administration of a research procedure). There is another reasonable explanation for the event (e.g. the patient's clinical condition, other concomitant treatments).
Not Related	There is no evidence of any causal relationship.
Not Assessable	Unable to assess on information available.

^{*} Where an event is assessed as possibly, probably or definitely related, the event is an AR.

15.4. Assessment of Severity

For unexpected AE/ARs the PI or designee should make an assessment of severity according to the following categories (Table 4).

Table 4. Categories of Severity for Adverse Events

Category (Severity)	Definition
Mild (Grade 1)	The adverse event is easily tolerated by the trial participant, causing minimal discomfort and not interfering with everyday activities.
Moderate (Grade 2)	The adverse event is sufficiently discomforting to interfere with normal everyday activities.
Severe (Grade 3)	The adverse event prevents normal everyday activities.
Life Threatening (Grade 4)	The adverse event has life threatening consequences; urgent intervention indicated.
Death (Grade 5)	The adverse event results in death.

15.5. Assessment of Seriousness

The PI or designee should make an assessment of seriousness, i.e. does the event fulfil any of the following criteria:

- Resulted in death
- Is life-threatening
- Requires hospitalisation or prolongation of existing hospitalisation
- Results in persistent or significant disability or incapacity
- Consists of a congenital anomaly or birth defect
- Is any other important medical event(s) that carries a real, not hypothetical, risk of one of the outcomes above

15.6. Assessment of Expectedness

The PI or designee should make an assessment of expectedness for AE/ARs (Table 5). The evaluation should be performed using the expected AE/AR listed above (see section 10.3: Safety Outcomes).

Table 5. Categories of Expectedness for Adverse Events

Expectedness	Definition
Expected	The AE/AR is listed in the protocol (section 10.3) as expected.
Unexpected	The AE/AR is not listed in the protocol (section 10.3)

Unexpected AE/AR and SAE/SAR should be reported in the appropriate AE/SAE forms.

15.7. Recording and Reporting of Urgent Safety Measures

If the PI, designee, or a member of study staff become aware of information that necessitates an immediate change in study procedure to protect trial participants from any immediate hazard, they should report the urgent safety measure immediately to the NICTU by phone and follow this up in an email to [contact].

The NICTU will report the urgent safety measure immediately to the CI and the Sponsor using the dedicated email addresses [contact] & [contact] and will liaise with the Sponsor and site to implement immediate procedures to eliminate any hazard. The NICTU will report any urgent safety measure immediately by phone to the REC and will follow this up with an email within three days of becoming aware of the urgent safety measure.

The PI or designee should respond to queries from the NICTU immediately to ensure adherence to these reporting requirements.

16. DATA MONITORING

16.1. Data Access

The agreement with each PI will include permission for trial related monitoring, audits and ethics committee review, by providing direct access to source data and trial related documentation. Each participant's confidentiality will be maintained, and their identity will not be made publicly available, to the extent permitted by the applicable laws and regulations.

16.2. Monitoring Arrangements

The NICTU will be responsible for trial monitoring. The frequency and type of monitoring (on site, remote or both) will be detailed in the monitoring plan and agreed by the Sponsor.

Before the trial starts at a participating site, training will take place to ensure that site staff are fully aware of the trial protocol and procedures. Checks will take place to ensure all relevant essential documents and trial supplies are in place. Monitoring during the trial will check the accuracy of data entered into the CRF against source documents, adherence to the protocol, procedures and GCP, and the progress of participant recruitment and follow up.

The PI or designee should ensure that the monitor can access all trial related documents (including source documents (i.e. data collection worksheets) that are required to facilitate the Source Data Verification (SDV) monitoring process. The extent of SDV will be documented in the monitoring plan.

17. REGULATIONS, ETHICS AND GOVERNANCE

17.1. Regulatory and Ethical Approvals

The trial will comply with the principles of GCP and the requirements and standards set out in the UK policy framework for health and social care research. The trial will be conducted in accordance with the ethical principles that have their origin in the Declaration of Helsinki. The protocol will be approved by a REC. The trial will be registered at https://www.isrctn.com before randomisation of the first participant.

17.2. Protocol Amendments

The investigators will conduct the study in compliance with the protocol given approval by the REC. Changes to the protocol may require ethics committee approval before implementation. The NICTU in collaboration with the Sponsor will submit all protocol modifications to the REC for review in accordance with the governing regulations.

17.3. Good Clinical Practice

The trial will be carried out in accordance with the principles of the ICH-GCP guidelines (www.ich.org). All members of the trial team will be required to have completed GCP training.

17.4. Protocol Compliance

The investigators will conduct the study in compliance with the protocol given approval by the REC. A protocol deviation is defined as an incident which deviates from the normal expectation of a particular part of the trial process. Any deviations from the protocol will be fully documented.

A serious breach is defined as a deviation from the trial protocol or GCP which is likely to effect to a significant degree:

- (a) the safety or physical or mental integrity of the participants in the trial; or
- (b) the scientific value of the trial.

The PI or designee is responsible for avoiding serious breaches to occur and, in the rare event of their occurrence, to ensure that serious breaches are reported directly to the NICTU using the dedicated email address ([contact]) within one working day of becoming aware of the breach. The NICTU will notify the Sponsor and CI immediately to ensure adherence to reporting requirements to REC where a serious breach has occurred.

Protocol compliance will be monitored by the NICTU who will undertake site visits to ensure that the trial protocol is adhered to and that necessary paperwork (e.g. CRFs, participant consent) is being completed appropriately.

17.5. Participant Confidentiality

In order to maintain confidentiality, all CRFs, questionnaires, study reports and communication regarding the study will identify participants by their assigned unique trial identifier and initials only. Participant confidentiality will be maintained at every stage and participant details will not be made publicly available to the extent permitted by the applicable laws and regulations.

17.6. Indemnity

Queen's University Belfast (QUB) will provide indemnity for any negligent harm caused to participants. QUB will provide indemnity for negligent and non-negligent harm caused to participants by the design of the research protocol by staff at QUB.

17.7. Record Retention

The PI will be provided with an ISF by the NICTU and will maintain all trial records according to GCP and the applicable regulatory requirements. The PI is responsible for the archiving of essential documents at their site in accordance with the requirements of the applicable regulatory requirements, Sponsor and local policies. The PI has a responsibility to allow the Sponsor to access archived data, which can be audited by the Sponsor on request. Following confirmation from the Sponsor, the NICTU will notify the PI when they are no longer required to maintain the files. If the PI withdraws from the responsibility of keeping the trial records, custody must be transferred to a person willing to accept responsibility. This must be documented in writing to the NICTU and Sponsor.

The TMF will be held by the NICTU in the BHSCT and the essential documents that make up the file will be listed in a SOP. On completion of the study, the TMF and study data will be archived by the NICTU according to the applicable regulatory requirements and as required by the Sponsor. The study data may be used in future research studies, and participants will be asked for their consent to allow this. All necessary ethical approval will be secured and in place where applicable for any future research studies.

